**Table 11: PFS2 Event Dates**

| Randomized Treatment | Condition  | PFS2 Event date  |
|----------------------|--|--|
| Placebo              | No Crossover   | Earlier of:
a) Death
b) 2 nd documented date of progression
c) Start date of 2 nd Non-protocol Anti-cancer therapy (NPACT)                                |
|                      | Crossover  | Earlier of:
a) Death
b) 1 st documented date of progression after initiation of cabozantinib
c) Start date of 1 st NPACT after initiation of cabozantinib |
| Cabozantinib         | Discontinue after 1 st documented disease progression     | Earlier of:
a) Death
b) 2 nd documented date of progression
c) Start date of 2 nd NPACT   |
|                      | Continue on open-label cabozantinib after 1 st documented | Earlier of:
a) Death
b) 1 st documented date of progression after starting open-  |

|  |                     |   |
|--|---------------------|---|
|  | disease progression | label cabozantinib
c) Start date of 1 st NPACT after starting open-label cabozantinib |
|--|---------------------|---|

The analysis of PFS2 will include all subjects in the ITT population done contemporaneously with the primary PFS analysis.

The summaries (median and 95% CI for median, stratified and unstratified HRs and their 95% CI) and graphs described in Section 8.1.2.6 will be generated for PFS2. Log-rank p-values will be calculated and will be presented for descriptive purposes; formal inferences will not be drawn.

#### **8.4.5 Biomarkers**

Baseline and changes from baseline for thyroglobulin will be summarized. Descriptive statistics (mean, standard deviation and median) will be presented by treatment group using all available data from protocol-defined time-points (i.e., baseline, W5D1, and W9D1).

A waterfall plot of best percentage change (i.e., best percentage decrease) from baseline will be presented for each treatment group using the OITT and ITT populations. In all calculations, best change from baseline will be based only on protocol-defined time-points i.e., baseline, W5D1, and W9D1.

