## **BIOMARKERS**

---

Available tumor tissue (from the most recently collected sample prior to subject participation in the study) will be obtained during screening or at enrollment for exploratory analysis to potentially evaluate biomarkers such as MET or RET and other pathway components (eg, RAS, BRAF), modulators associated with the mechanism of action of cabozantinib.

Blood samples to evaluate plasma and/or serum biomarkers and circulating DNA (ctDNA) may be collected prior to first dose (W1D1) and postdose at specified time points.

At selected sites, blood samples may be collected for the enumeration of circulating tumor cells (CTCs) prior to first dose (W1D1) and postdose at specified time points. Molecular markers potentially related to DTC and/or study treatment mechanism(s) of action may also be assessed in these CTC samples.

A blood sample will be collected pre-dose on the day of first dose (W1D1) for genotyping/single nucleotide polymorphism/copy number variation analysis to correlate genetic variation with PK, safety, tolerability of and response to study treatment.

Detailed instructions for sample processing, storage, and shipment will be provided in the translational medicine laboratory manual.

Collection of these samples may be halted early or sampling frequency may be reduced at the discretion of the Sponsor. Biomarker analyses may not be performed at the time of the primary endpoint analyses and may extend beyond the end of the study.

No pharmacodynamic or biomarker samples will be collected for subjects who transition to the Crossover Phase or if the study transitions to the Maintenance Phase.

Note: Serum Tg levels will be analyzed as part of the routine clinical laboratory assessments. Results of serum Tg analyses will not be shared with investigators to avoid bias in the study.

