### **9.7 Additional Endpoints**

Details of the planned analyses of these endpoints will be provided in the SAP:

- Duration of objective tumor response
- Relationship of baseline and postbaseline changes in biomarkers, serum Tg, and CTCs and/or ctDNA with treatment and/or clinical outcome assessments may be performed
- Health care resource utilization

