| Thyroid function test by central lab e (Section 5.7.5)           | ≤ 28 days  | X d (prior to first dose)                 | X        | X    |      | X    | Every 8 weeks (W17D1, W25D1, etc)    | X  |                    |
| Thyroglobulin by central lab f (Section 5.7.5)                   | ≤ 28 days  |  |          | X    |      | X    | Every 8 weeks (W17D1, W25D1, etc)    |  |                    |
| Follicle stimulating hormone by central lab e, g (Section 5.7.5) | ≤ 28 days  |  |          |      |      |      |                                      |  |                    |

| Assessment:  | Pre-randomization                                | Post-randomization  |   |      |      |      |                                      |  |                    |
|--|--|---|---|------|------|------|--------------------------------------|--|--------------------|
|  | Screening a
(before randomization) | W1D1
(≤ 3 days after randomization)  | (± 3 Days)  |      |      |      | After Beginning of Week 9 (± 5 days) | 30-Day Post-Treatment Follow-Up (+14 days) | Extended Follow-Up |
|  |  |   | W3D1  | W5D1 | W7D1 | W9D1 |                                      |  |                    |
| Tumor tissue h (Section 5.7.10)                                   | X  | X   |   |      |      |      |                                      |  |                    |

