#### **2.3.2 Additional Endpoints**

- Overall survival (OS)
- Duration of objective tumor response
- Safety and tolerability (see Section 9)
- Pharmacokinetics (PK) (see Section 8.4.8)
- Relationship of baseline and post-baseline changes in serum thyroglobulin (Tg), will be performed (see Section 8.4.5)
- Change in mobility, self-care, usual activities, pain/discomfort, anxiety/depression, and global health as assessed by the EuroQol Health questionnaire instrument (EQ-5D-5L) (see Section 8.4.6)
- Health care resource utilization (see Section 8.4.7)

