## **5.6 Baseline Laboratory Values**

Descriptive statistics will be provided for baseline laboratory values for TSH and thyroglobulin for the OITT and ITT populations. In addition, TSH baseline values (mUI/L) will also be summarized by frequencies and percentages of subjects in the following categories for the same populations.

- $\leq 0.1$  mUI/L
- $0.1 - < 0.5$  mUI/L
- $\geq 0.5$  mUI/L

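### SAP 8.4.5 misstates the protocol's thyroglobulin schedule as ending at Week 9, so its summaries and waterfall plot leave out later scheduled draws

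*Combined protocol and SAP*

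**What the plan says.** Protocol Appendix A gives thyroglobulin its own row: a screening draw within 28 days before randomization, then W5D1 and W9D1, and after Week 9 "Every 8 weeks (W17D1, W25D1, etc"). The synopsis section on biomarkers separates this test from the exploratory blood samples: "Serum Tg levels will be analyzed as part of the routine clinical laboratory assessments". Table 5-1 lists it among the central laboratory tests.

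Protocol 9.7 leaves the analysis details to the SAP and makes the work optional: "Relationship of baseline and postbaseline changes in biomarkers, serum Tg, and CTCs and/or ctDNA with treatment and/or clinical outcome assessments may be performed". SAP 2.3.2 lists the endpoint ("Relationship of baseline and post-baseline changes in serum thyroglobulin") and says that it will be done.

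SAP 8.4.5 is the only section that specifies a post-baseline thyroglobulin analysis. Its descriptive statistics are to be produced "using all available data from protocol-defined time-points (i.e., baseline, W5D1, and W9D1"). For the waterfall plot of best percentage change, in the OITT and ITT populations, the restriction is explicit: "best change from baseline will be based only on protocol-defined time-points i.e., baseline, W5D1, and W9D1".

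The only other analysis that names thyroglobulin is the baseline summary in SAP 5.6: "Descriptive statistics will be provided for baseline laboratory values for TSH and thyroglobulin for the OITT and ITT populations".

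**The concern.** Both statements in SAP 8.4.5 equate the protocol-defined time-points with baseline, Week 5 and Week 9. The protocol defines more. A programmer following 8.4.5 literally would leave out W17D1, W25D1 and later visits while believing that the protocol schedule had been covered in full. The section would also be at odds with itself, since it promises all available data from the protocol's time-points and then names only some of them.

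What is at stake is the time span of a listed additional endpoint. W9D1 is Day 57, close to the first scheduled post-randomization scan (8 weeks ± 7 days). A response must be confirmed at least 28 days after it is first seen, so on the scheduled visits the 8.4.5 analysis stops before a response could be confirmed. A low point after Week 9 could not enter the best-change plot, and later visits would be missing from that section's change-from-baseline summaries.

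**Working it through.** The plan states no figure to reproduce. The check is a comparison of texts followed by a count of scheduled visits.

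**Comparison.**
- Thyroglobulin in Appendix A: screening, W5D1, W9D1, then W17D1, W25D1 and every 8 weeks.
- SAP 8.4.5: baseline, W5D1, W9D1.
- Plasma biomarker, ctDNA and CTC rows in Appendix A: post-dose samples at W5D1 and W9D1 only. The SAP list matches these rows, so it may have been carried over from them. That is an inference.
- The Sponsor's option to halt or reduce sampling (synopsis and protocol 5.7.10) is written for the biomarker samples. The synopsis treats thyroglobulin separately as a routine laboratory test.
- SAP 4.9, on changes to planned analyses, adds PFS2 and does not mention a thyroglobulin cut-off.

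**Count.** Inputs: expected average treatment of 9 months (protocol 3.2); 1 month = 30.4375 days (SAP 4); draws at weeks 5, 9, 17 and every 8 weeks thereafter (Appendix A). The day of the draw at week *w* is 7 × (*w* − 1) + 1, which gives Days 29, 57, 113, 169, 225, 281 and so on. A draw counts if that day is no later than months × 30.4375.

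At 9 months: 9 × 30.4375 = 273.9 days. Week 33 (Day 225) falls inside and Week 41 (Day 281) outside. The draws are W5, W9, W17, W25 and W33, five in all. SAP 8.4.5 uses 2 (2/5 = 40%) and omits 3. The other durations below are assumed, to show the range; 5.5 months is the planned placebo median PFS, used as a reference point.

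| Months on treatment | Days | Scheduled post-baseline draws | Used by 8.4.5 | Omitted |
|---|---|---|---|---|
| 3 | 91.3 | 2 | 2 | 0 |
| 5.5 | 167.4 | 3 | 2 | 1 |
| 6 | 182.6 | 4 | 2 | 2 |
| 9 | 273.9 | 5 | 2 | 3 |
| 12 | 365.2 | 7 | 2 | 5 |
| 18 | 547.9 | 10 | 2 | 8 |

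These are nominal visit days. At 5.5 months the W25D1 visit (Day 169) is only 1.6 days away and inside its ±5-day window, so that row could be 4 draws with 2 omitted.

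**Could another section recover the later values?** SAP 9.5.2 summarises continuous laboratory results by scheduled visit, as actual values and as changes from baseline. Thyroglobulin is not in the SAP 9.5.1 list. That list covers treatment-emergent abnormalities, however, and does not bound 9.5.2: blood urea nitrogen is plotted and free T4 is summarised under 9.5.2, and neither is in the list. So 9.5.2 may cover thyroglobulin, but it does not say so. It would report in the Safety and O-Safety populations, whereas the 8.4.5 waterfall uses OITT and ITT.

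**The case against.** **Unequal follow-up.** Best change over all visits favours the arm followed longer, because more draws mean more chances of a low value, and planned median PFS is 9.0 months on cabozantinib against 5.5 on placebo. Stopping at Week 9 gives the arms nearly equal opportunity. This stands as a reason to keep a Week 5/Week 9 waterfall. Which version is the main display is a trade-off.

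**Selection at later visits.** From about Week 8, progression confirmed by the BIRC can lead to unblinding and crossover, and the crossover schedule (Table 20-1) has no thyroglobulin row. Later placebo means would come increasingly from subjects who have not progressed. This weakens between-arm comparisons after Week 9, but it is no reason to withhold descriptive by-visit results shown with their denominators. The SAP does not offer either argument itself.

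**Low stakes.** The protocol makes these analyses optional, everything beyond the two primary hypotheses is exploratory, and 8.4.5 contains no test. Neither document plans an analysis of thyroglobulin rises near progression. All of this stands, and it keeps the point minor.

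**Stronger readings.** A reader might infer that every thyroglobulin analysis stops at Week 9 and that later data are thrown away. The documents do not support that: the samples are still drawn and stored in the database, and SAP 9.5.2 may report them by visit.

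**Conclusion.** The point holds as an inconsistency between the SAP and the protocol. SAP 8.4.5 describes as protocol-defined a list that omits every scheduled draw after Week 9, and gives no reason. Its change summaries and best-change plot therefore leave out those values as written. Whether later visits appear elsewhere is ambiguous, not excluded.

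The size depends on time on treatment: nothing is lost at 3 months, 1 of 3 draws at 5.5 months and 3 of 5 at 9 months, assuming nominal visit days and every draw taken. These are schedule counts for a single subject of that duration. A reader might take the 9-month figure to mean that 60% of the trial's thyroglobulin data go unused. It does not mean that, because 9 months is an expected average over subjects whose durations will differ and is not split by arm.

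The consequence is confined to one exploratory, descriptive endpoint. ORR, PFS and control of type I error are unaffected.

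**What to change.** In SAP 8.4.5, list the time-points as baseline, W5D1, W9D1 and every 8 weeks thereafter (W17D1, W25D1 and so on) during the Blinded Period, the period that SAP 4.1 uses for efficacy summaries other than OS. Present actual values and changes from baseline at each of these visits, with the number of subjects per arm.

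The Week 5/Week 9 waterfall may stay as the equal-follow-up display, labelled as restricted to Week 9 and not as covering all protocol-defined time-points. An all-visit version is an optional addition. If a Week 9 cut is intended for the whole section, state it and justify it under SAP 4.9. In either case, say whether the by-visit summaries in SAP 9.5.2 include thyroglobulin.

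The cost is SAP wording and some extra table rows; the central laboratory already runs the samples. The drawback is that later visits will hold fewer and more selected subjects, especially on placebo, so a note should advise caution in comparing arms there.

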#### **8.4.6 Health-Related Quality of Life (HRQOL)**

Health-related quality of life (HRQOL) will be assessed by the EuroQol Health questionnaire instrument (EQ-5D-5L). The questionnaire will be self-completed by the subjects at various time points until disease progression and will provide a generic measure of health for clinical appraisal (see protocol Section 5.7.7). The EQ-5D-5L questionnaire has two pages: a descriptive page which assesses on an increasing severity scale of 1-5 changes in the following five questions (dimensions): mobility, self-care, usual activities, pain/discomfort, and anxiety/depression. The second page has a 0-100 visual analogue scale (VAS) which records the subjects self-rated health between 100 (best health you can imagine) and 0 (worst health you can imagine) and serves as quantitative measure of health by the subject (see protocol Appendix F and EQ-5D-5L User Guide, Version 3.0 [2019]).

To compare the two treatment arms the following summaries are planned at each time point for each of the 6 questions:

Within each treatment arm:

- Descriptive statistics (number of observations, mean and standard deviation)
- Rate of completion for the questionnaire at each time point. This is defined as total number of subjects who answered all questions on the EQ-5D-5L questionnaire / the expected total number of subjects still on study at the visit
- Mean change from baseline at each time point and the corresponding 95% CI and p-value from one-sample t-test
- Effect size for change from baseline within arm, calculated as (mean of change in score/pooled standard deviation for baseline scores). An effect size greater than  $\geq 0.3$  will be considered potentially clinically meaningful
- Shift in the severity scale since baseline

Across treatment arms

- The difference in the effect sizes will be presented
- Difference in mean change from baseline for the questions at the time point will be evaluated by a two sample t-test
- Line plots for mean $\pm$ standard error and the corresponding mean for change from baseline over time. Data from both treatment arms will be displayed on the same plot. In addition, these plots will also show the average state of the subjects at 3 landmark points, namely, around end of treatment, around progression and around 30 days post treatment follow-up for the two treatment arms
- Percentage of subjects in Level 1 (no problem) vs. Levels 2-5 (any problems) will be summarized over time
- Percentage of subjects with any problems (Level 2-5) will be compared between the treatment arms using a bar chart

The EQ-5D-5L may be converted into a single index (EQ-Index) value normalized across different countries where the index is validated. See Appendix D for conversion details. For EQ-VAS and EQ-Index, descriptive statistics for change from baseline at each time will be presented. Plots for mean $\pm$ standard error and mean change from baseline $\pm$ standard error over all time points for the two treatment arms will be generated.

Repeated-measures mixed-effects models will be used to explore treatment differences over time for the blinded phase of the study only. These analyses will include the outcome

variable of QOL score change from baseline. The predictors (fixed effects) will be the baseline scores, treatment arms, visit, and randomization strata described in Section 2.5. The individual subject nested within the planned treatment arm will be the random effect. All available data will be included for the analysis. The estimated least squares means for the two treatment arm and their difference, the p-values comparing the 2 treatment arms and the effect size will be presented. No adjustment will be made for multiple comparisons. An effect size of differences in the  $\geq 0.3$  range will be considered potentially clinically meaningful. All summaries will be provided for the OITT and ITT populations.

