| HRQOL EQ-5D-5L i (Section 5.7.7)                                  |  | X
(prior to first dose)  | 
Every 4 weeks through W25D1 followed by every 8 weeks.
 
These assessments are to be performed regardless of whether study treatment is given, reduced, held, or discontinued. HRQOL will no longer be collected for subjects who transition to the Crossover Phase or if the study transitions to the Maintenance Phase.
 |      |      |      |                                      |  |                    |

| Assessment:  | Pre-randomization   | Post-randomization  |            |      |      |      |                                      |  |                    |
|--|---|---|------------|------|------|------|--------------------------------------|--|--------------------|
|  | Screening a
(before randomization)  | W1D1
(≤ 3 days after randomization)  | (+ 3 Days) |      |      |      | After Beginning of Week 9 (± 5 days) | 30-Day Post-Treatment Follow-Up (+14 days) | Extended Follow-Up |
|  |   |   | W3D1       | W5D1 | W7D1 | W9D1 |                                      |  |                    |
| PK blood samples j (Section 5.7.9)                              |   |   | X          | X    |      | X    |                                      |  |                    |
| Pharmacogenetic blood sample k (Section 5.7.10)                 |   | X
(prior to first dose)  |            |      |      |      |                                      |  |                    |
| Plasma biomarker samples (Section 5.7.10)                                  |   | X
(prior to first dose)  |            | X    |      | X    |                                      |  |                    |
| ctDNA (Section 5.7.10)   |   | X
(prior to first dose)  |            | X    |      | X    |                                      |  |                    |
| CTC blood samples (Section 5.7.10)   |   | X
(prior to first dose)  |            | X    |      | X    |                                      |  |                    |
| Concomitant medication (Section 7)   | Document concomitant medication (including transfusions) taken from 28 days before randomization through 30 days after the date of the decision to discontinue study treatment  |   |            |      |      |      |                                      |  |                    |

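### The HRQOL mixed model is meant to explore differences over time but has no treatment-by-visit term, so changing effects are examined only in unadjusted analyses outside it

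*Combined protocol and SAP*

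**What the plan says.** The aim, in SAP 8.4.6, is: "Repeated-measures mixed-effects models will be used to explore treatment differences over time for the blinded phase of the study only". The outcome is change in score from baseline. The fixed part is: "The predictors (fixed effects) will be the baseline scores, treatment arms, visit, and randomization strata described in Section 2.5". The random part is: "The individual subject nested within the planned treatment arm will be the random effect". The sentence on the planned output opens: "The estimated least squares means for the two treatment arm and their difference, the p-values comparing the 2 treatment arms and the effect size will". Visits are not mentioned in that output, and a difference in effect size of 0.3 or more counts as potentially meaningful. The summaries are for both the OITT and ITT populations.

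Protocol 9.4 leaves the HRQOL analysis to the SAP, and no treatment-by-visit term appears elsewhere in either document.

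Outside the model, SAP 8.4.6 lists between-arm summaries at each time point for six questions. They include this one: "Difference in mean change from baseline for the questions at the time point will be evaluated by a two sample t-test". They also include differences in effect size and line plots with both arms overlaid. Protocol 9.4 counts the global health score as the sixth question, so the VAS is covered. For EQ-Index, the by-time-point material is descriptive statistics and plots only.

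The questionnaire schedule in protocol Appendix A is: "Every 4 weeks through W25D1 followed by every 8 weeks".

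**The concern.** An additive model in arm and visit assumes that the treatment difference is the same at Week 5 as at Week 49. Here that assumption is doubtful. Protocol 6.7.1 says adverse events may come in the first few weeks and lists diarrhea, vomiting, PPE and mucosal inflammation among the early ones. A benefit from delayed progression would come later. A model meant to show how the arms differ over time therefore cannot show a difference that changes, and its single figure depends on how many subjects happen to contribute at each visit.

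At stake is the only between-arm HRQOL analysis that adjusts for baseline and strata. For EQ-Index it is also the only planned between-arm test. Protocol 1.5.1 intends the EQ-5D-5L results to support the primary endpoints, so the estimate is likely to be read.

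**Working it through.** The documents give no figure for this model, so there is none to reproduce. The check is algebra followed by an illustration.

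**1. Algebra.** As specified, the mean change at visit k is baseline term + a·arm + visit effect v(k) + strata terms. The arm contrast at visit k is (a + v(k)) − v(k) = a, for every k. A random subject effect has mean zero, so it cannot make the mean difference vary by visit. With a treatment-by-visit term the contrast is a + g(k), which can vary.

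**2. Visit density.** From Appendix A, the post-baseline visits through Week 49 are W5, W9, W13, W17, W21 and W25 (six), then W33, W41 and W49 (three). Six of nine fall in the first 24 weeks even with no dropout.

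**3. What the single figure averages.** When the true differences d(k) vary, the fitted coefficient estimates Σ w(k)·d(k), with weights set by who is still observed. Inputs from the protocol:
- 200 cabozantinib and 100 placebo subjects (9.10)
- median PFS of 9.0 and 5.5 months (9.10)
- questionnaires continuing to 8 weeks after progression (synopsis, HRQOL)

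Assumptions that are not in the documents:
- exponential attrition at those medians, unrelated to outcome
- subject SD 0.6 and residual SD 0.7, in baseline-SD units
- visits W5 to W25 only, and the effect profiles below

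Generalised least squares on these inputs gives weights for W5 to W25 of 0.213, 0.213, 0.176, 0.150, 0.131 and 0.117. Equal weighting would be 1/6 = 0.167 each.

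| True difference, W5 to W25 | Equal average | Model as written |
|---|---|---|
| -0.4, -0.3, -0.1, 0.1, 0.3, 0.4 | 0/6 = 0.00 | -0.085 - 0.064 - 0.018 + 0.015 + 0.039 + 0.047 = -0.07 |
| 0, 0, 0.1, 0.2, 0.4, 0.5 | 1.2/6 = 0.20 | 0.018 + 0.030 + 0.052 + 0.059 = 0.16 |
| 0.2 throughout | 0.20 | 0.20 |

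A simulation on the same assumptions (60 data sets per profile) gave -0.07, 0.16 and 0.20. Refitted with arm-by-visit terms, it gave -0.43, -0.28, -0.09, 0.07, 0.29, 0.39 for the first profile; 0.01, 0.01, 0.10, 0.20, 0.40, 0.45 for the second; and 0.19 to 0.22 for the third. In the second profile the single figure lies below the SAP's 0.3 mark, although the true difference is 0.4 and 0.5 at the last two visits.

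**4. Thin late visits.** Suppose instead that collection ends at progression. W25 is 24 × 7/30.4375 = 5.52 months and W49 is 11.04 months. The proportions remaining are:
- placebo: 0.5^(5.52/5.5) = 50% at W25 and 0.5^(11.04/5.5) = 25% at W49
- cabozantinib: 0.5^(5.52/9) = 65% at W25 and 0.5^(11.04/9) = 43% at W49

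At W49 that is about 25 of 100 placebo subjects in the ITT population. In the OITT population it is about 8 of 33.

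**The case against.** The strongest reply is that the plan already looks at each visit. A reader might infer from the model that opposite early and late effects would cancel and be reported as no difference. The documents do not support that. For the six questions, including the VAS, the t-tests by time point, the effect-size differences and the overlaid plots would show a crossing pattern, and EQ-Index has plots and descriptive summaries. This stands, and it limits the point. What remains is that those comparisons are not adjusted for baseline or strata, do not use the repeated measures jointly, and for EQ-Index include no between-arm test.

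A second reply is that differences over time may mean an average over follow-up, which an additive model does give and which fits the stated output. That reading is possible. But the SAP does not say so, and it does not fix how visits are weighted.

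A third is that the sizes above are invented. They are assumptions. They show the mechanism, not what to expect in this trial.

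A reader might also infer that the interaction cures the loss of placebo questionnaires at crossover. It does not. That is a missing-data problem, and the term only moves it to sparse late contrasts. Nor are baseline-by-visit terms or an unstructured covariance required by this point. They are modelling preferences.

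**Conclusion.** The point holds in limited form. As specified, the model cannot estimate a treatment difference that changes over visits, and its single estimate leans toward early visits. Visit-specific differences would be seen in the report, but only in unadjusted or descriptive form. In the illustration the lean is small (-0.07 against 0, and 0.16 against 0.20). The larger loss is the visit profile itself. If the true difference is constant, the two models agree. The algebra rests on the SAP text alone; the sizes rest on the assumed profiles, variances and attrition. SAP 8.2 makes every efficacy evaluation beyond the two primary tests exploratory, so the ORR and PFS conclusions do not depend on this. It is a minor, worthwhile improvement.

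**What to change.** In SAP 8.4.6, add treatment-by-visit to the fixed effects. Report LS mean differences with confidence interval and effect size at each visit, plus a pre-specified, equally weighted average over a stated set of visits. Choose that set so that enough placebo subjects are expected at its last visit. If only one overall difference is wanted, reword the aim as an average across visits and state the weighting.

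The cost is a sentence or two in the SAP and somewhat less precision at single visits. Late-visit intervals will be wide, most of all in the OITT population, where about 8 placebo subjects might remain at Week 49 under the assumption above. SAP 9.9 already foresees an amendment, and SAP 4.9 requires substantive changes to be documented before unblinded analyses, so the change can go in there.
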